9.1 Primary and Secondary Hypotheses and Endpoints

Aim 1: Develop and evaluate the usability of cancer-specific and motivational tools in the mobile app (Phase 1).

AYA survivors will help design the functionality requirements for the initial prototype. An experienced app development company will program the app with identified tools such as goal setting, self-monitoring, exercise instructions, and social networking. Usability testing will be conducted in an iterative manner with AYA survivors, refining the app based on user feedback (total $n = 20$).

Aim 2: Evaluate the feasibility of the technology-enhanced (electronic accelerometer + app + 8 weekly group sessions) fitness program in a pilot RCT (Phase 2).

Hypothesis 1: AYAs will agree to participate in the program, demonstrate engagement in the program via $> 80\%$ attendance at group-based sessions, and use one or more components of the app at least weekly.

Aim 3: Determine the effectiveness of the technology-enhanced fitness program on participants' cardiorespiratory fitness and muscular strength.

Hypothesis 2: Participants in the intervention group will demonstrate greater improvement in cardiorespiratory fitness (objective submaximal treadmill testing) and muscular strength (objective 10-repetition max testing) from baseline than wait-list control participants at the post-intervention assessment (Time 3).

Aim 4: Examine the effects of the program on secondary outcomes of health-related quality of life (HRQOL), and fatigue.

Hypothesis 3: Participants in the intervention group will demonstrate greater improvement in HRQOL (PedsQL Generic Core Scale) and fatigue (PedsQL Multidimensional Fatigue Scale) from baseline than the wait-list control group at the post-intervention assessment (Time 3).

9.2 Sample Size Justification

The focus of this work is to determine feasibility and estimate the effect size. Since this is a feasibility study, we intend to enroll 88 patients and expect 10% attrition, resulting in 80 patients with evaluable data. With a sample size of 40 per group and alpha set at .05, we calculate that we will have 80% power to detect a medium effect size (Cohen's $d = .32$) for differences between groups in muscular strength scores using ANCOVA. While we recognize that this study is underpowered for small effects, the primary aim is feasibility.

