Aim 3: This aim is to determine the effectiveness of the program on the primary outcomes, objectively-measured cardiorespiratory fitness and muscular fitness. The primary hypothesis is that participants in the intervention group will demonstrate greater improvement in cardiorespiratory fitness (measured via the Submaximal Treadmill test) and muscular fitness (measured via the objective 10-repetition max tests) from baseline than wait-list control participants at the 3-month assessment (after the intervention group completes TLC FIT). To test this hypothesis, the two groups’ outcome scores at the post assessment will be compared using ANCOVA, controlling for baseline scores. To account for enrollment in cohorts, cohort will be included as a covariate and removed if not significant. The primary analysis will be performed on an “intent-to-treat” basis; i.e., once a subject is randomized, data on that subject will be analyzed according to assignment, regardless of the degree to which the subject participates.

Aim 4: This aim will evaluate the effects of the program on the secondary outcomes of HRQOL and fatigue. We will test the hypothesis that participants in the intervention group will demonstrate greater improvement in HRQOL and fatigue from baseline than the wait-list control group at the 3-month assessment using ANCOVA.

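### Section 9.2's 80% power for Cohen's d = .32 does not follow from the inputs it gives; .32 is most likely Cohen's f, and the metric, sidedness and assumed baseline correlation need stating

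*Combined protocol and SAP*

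**What the plan says.** Section 9.2 (Sample Size Justification) plans 88 enrolled and 80 evaluable participants. Its power statement begins "With a sample size of 40 per group and alpha set at .05" and goes on to claim "80% power to detect a medium effect size (Cohen's $d = .32") "for differences between groups in muscular strength scores using ANCOVA". It then concedes that "we recognize that this study is underpowered for small effects" and says that feasibility is the primary aim.

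Section 9.4, Aim 3, describes the test: the groups' scores at the 3-month assessment "will be compared using ANCOVA, controlling for baseline scores". Cohort enters as a further covariate and is dropped if not significant.

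Neither section gives a correlation between baseline and follow-up, a residual SD or the sidedness of the test. Neither says whether d is scaled to the raw SD or to the SD left after baseline adjustment.

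**The concern.** Forty per group is a familiar size, and an unadjusted two-group comparison of that size needs a standardised difference well above .32 for 80% power. The adjective does not fit either. By the usual benchmarks (d of .2 small and .5 medium; f of .25 medium), .32 lies nearer to small than to medium on the d scale, but near medium on the f scale.

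This is the only power statement in the plan. Feasibility is the declared focus, but Section 6 and Section 9.4 (Aim 3) call the fitness measures primary outcomes and attach a hypothesis test to them. A reader judging what that test can show has only this sentence to go on. If .32 is f, the detectable difference on the d scale, before any gain from baseline, is twice what the sentence says.

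**Working it through.** **Inputs.** From Section 9.2: n = 40 per group, alpha = .05, target power 80%, effect .32 labelled d, ANCOVA. From Section 9.4: adjustment for the baseline score. Assumed because not stated: two-sided test (one-sided also shown), and a baseline-to-Time 3 correlation r from 0 to .9.

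**1. The plan's figure with its inputs as labelled (no gain from baseline).**
- Noncentrality = d × sqrt(n/2) = .32 × sqrt(20) = 1.431.
- Normal approximation, two-sided: Φ(1.431 − 1.960) = Φ(−0.529), about 29.8%. The exact noncentral t with 78 df gives 29.3%.
- One-sided, exact: 41.1%.
- Two-sided with all 88 participants analysed (44 per group): 31.7%.

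None of these is near 80%. By the normal formula, d = .32 without covariate gain would need 2 × (2.802/.32)², or 154 per group, two-sided (121 one-sided).

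**2. What 40 per group detects with 80% power (no gain from baseline).**
- Normal approximation: (1.960 + 0.842) × sqrt(2/40) = 0.626. Exact t: d = 0.634 (0.561 one-sided).

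**3. Reading .32 as Cohen's f.**
- For two equal groups f = d/2 = 0.634/2 = 0.317, which rounds to .32.
- Noncentral F with N = 80, two groups, one covariate and noncentrality N × f²: power at f = .32 is 80.7%, and 80% is reached at f = 0.317.
- f = .32 corresponds to d = 0.64 in units of the baseline-adjusted SD.

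This reading reproduces the stated power. A paired test on all 80 participants with d = .32 also gives 80.7%, but Section 9.2 specifies a comparison between groups.

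**4. Reading .32 as d on the raw SD, with baseline adjustment.** ANCOVA shrinks the SD by sqrt(1 − r²), so the effective effect is .32/sqrt(1 − r²), and the raw-SD difference detectable with 80% power is 0.634 × sqrt(1 − r²).

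| r | Two-sided power at d = .32 | Detectable d, 80% power |
|---|---|---|
| 0 | 29% | 0.63 |
| .5 | 37% | 0.55 |
| .7 | 51% | 0.45 |
| .8 | 65% | 0.38 |
| .86 | 79% | 0.32 |
| .9 | 90% | 0.28 |

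The r needed for 80% power solves 0.634 × sqrt(1 − r²) = .32. So sqrt(1 − r²) = 0.505 and r is about .86. One-sided, .32/0.561 = 0.570 and r is about .82.

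**The case against.** The strongest reply is that the planned test is a baseline-adjusted ANCOVA, so an unadjusted calculation does not describe it. That stands. A reader might infer from step 1 that the trial simply has 29% power at d = .32 and can detect only d of about .63. The documents do not support that as a flat statement. Those figures hold if r is zero, or if d is scaled to the residual SD. With a raw-SD d and a high enough r, the stated 80% is attainable, and nothing in the documents excludes such an r. Strictly, the relevant quantity is all the variance explained by the covariates, including cohort where it is retained, so r here stands for the multiple correlation.

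It is also fair to say that if .32 is f, the calculation itself is sound and only the symbol is wrong. But the documents never mention f, so that remains an inference from the numerical match and the adjective.

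Three further readings are tempting and fail:
- That the trial is underpowered for medium effects as well. At a raw-SD d of .5, two-sided power is about 60% at r = 0, 72% at r = .5 and 87% at r = .7, and it passes 80% at r of about .62. A blanket statement would be false for higher r.
- That the planning value of .32 will carry into the future R01. Section 10.5 says that data from this trial will be used for that sample size.
- That 80 evaluable from 88 is a material error. 88 × 0.9 = 79.2, and with 39 and 40 per group the detectable d moves only from 0.634 to 0.638.

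Finally, pilot status and the stress on feasibility reduce the consequence. They do not make the printed figure reproducible.

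**Conclusion.** The power statement is wrong as written: the inputs printed in Section 9.2 give about 29% two-sided, or 41% one-sided, where 80% is claimed. Only added information closes the gap. The likelier explanation is a mislabelled metric, with .32 being f and d about .64 on the baseline-adjusted scale, because both the number and the word 'medium' point that way. The alternative, a raw-SD d of .32, needs an unstated correlation of about .86 two-sided or .82 one-sided. Under that alternative the word 'medium' still does not fit.

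The conclusion assumes equal groups of 40, alpha .05 and the usual ANCOVA variance reduction. It does not establish the actual power of the planned test, which depends on a correlation that the documents do not give. Nor does it show that the trial is too small for its feasibility purpose.

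**What to change.** Restate the power sentence in Section 9.2 so that it names the effect-size metric, the sidedness of alpha and the assumed baseline-to-Time 3 correlation.

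- If .32 is f and the test is two-sided, write: *Cohen's f = .32 (d of about .64 on the baseline-adjusted SD scale); with baseline correlation r, the detectable raw-SD difference is about 0.634 × sqrt(1 − r²).*
- If .32 is d, say that it is in raw-SD units, state the assumed r and its source, and replace 'medium' with a description that fits.

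In either case, reword the caveat about underpowering so that it follows from the restated detectable effect.

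The cost is a few sentences in one section. The stated sensitivity may look less favourable. Enrolment, randomisation and the analysis model stay as they are.

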9.3 Methods for Masking, Randomization and Stratification

A randomization scheme will be determined prior to the start of recruitment in accordance with the Standard Operating Procedures of the Biometrics Division of the Rutgers Cancer Institute of New Jersey. Randomization will be stratified by cohort (due to recruitment in waves) and age (13-17 and 18-25). Randomization will occur after baseline measures are completed. Trained personnel who conduct the assessments will be masked to the assignment (intervention vs. WLC) of the participants.

9.4 Statistical Analysis

Preliminary data analysis will include descriptive statistics, assessment of reliability of surveys (Cronbach's alpha), and evaluation of distributions of each variable. If distributions are skewed or fail to meet assumptions for parametric analyses, transformations or non-parametric procedures will be used as appropriate. Strategies for handling missing data will

be chosen based on the type, nature, and extent of the problem, and could range from replacing a single item on a scale with the mean of the subscale, dropping a subscale/measure, or multiple imputation for the primary endpoint.

Aim 1: Participants will initially provide input for development based on individual interviews, which will be transcribed and analyzed to identify desirable components for inclusion in the app. For usability testing, participants are given a defined set of tasks to complete and observed to determine the ease with which participants can navigate tools and success in utilizing various aspects of the app (e.g., error rates, time to complete tasks). Participants will also provide qualitative and quantitative feedback regarding satisfaction with features, ease of use, and likeability of the app. Usability tests will be completed using a rapid iterative procedure, in which design changes are completed after receipt of a set of participants’ feedback and then tested with the next set of participants. The app will be refined to eliminate issues that impede usability. A total n of 20 participants is anticipated to achieve saturation on issues identified during testing.

Aim 2: Feasibility will be evaluated using enrollment rates, assessment completion rates, attendance at weekly sessions, adherence to exercise prescription outside of sessions, and usage of the electronic accelerometer and app. The primary hypothesis is that AYAs will agree to participate in the intervention and demonstrate engagement via > 80% attendance at group-based sessions and use one or more components of the app at least weekly. Descriptive analyses (means, frequencies) will be used.

Aim 3: This aim is to determine the effectiveness of the program on the primary outcomes, objectively-measured cardiorespiratory fitness and muscular fitness. The primary hypothesis is that participants in the intervention group will demonstrate greater improvement in cardiorespiratory fitness (measured via the Submaximal Treadmill test) and muscular fitness (measured via the objective 10-repetition max tests) from baseline than wait-list control participants at the 3-month assessment (after the intervention group completes TLC FIT). To test this hypothesis, the two groups’ outcome scores at the post assessment will be compared using ANCOVA, controlling for baseline scores. To account for enrollment in cohorts, cohort will be included as a covariate and removed if not significant. The primary analysis will be performed on an “intent-to-treat” basis; i.e., once a subject is randomized, data on that subject will be analyzed according to assignment, regardless of the degree to which the subject participates.

Aim 4: This aim will evaluate the effects of the program on the secondary outcomes of HRQOL and fatigue. We will test the hypothesis that participants in the intervention group will demonstrate greater improvement in HRQOL and fatigue from baseline than the wait-list control group at the 3-month assessment using ANCOVA.

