Recruitment will occur in waves, such that 10-20 participants will be randomized within cohorts, and each arm will have 5-10 patients at a time. After obtaining informed consent/assent, participants will complete baseline assessments (Time 1) conducted either in group formats or individually as done in our preliminary study. The assessments will be conducted by trained research personnel. Participants will then be randomized to either TLC FIT (8 group sessions + electronic accelerometer + App) or wait-list control (WLC). Randomization will be stratified by cohort (since enrolled in waves) and age (13-17 vs. 18-25). All participants will be asked to complete assessments at Time 2 (~2 months, after the in-person sessions are completed for the TLC FIT group), Time 3 (~3 months; after the full in-person plus app intervention for TLC FIT group), Time 4 (~6 months), and Time 5 (~9 months; after the waitlist control participants receive the intervention). Waitlist control participants will also be asked to complete the objective fitness tests during the last session of the in-person groups; they will be given feedback on their results but no additional monetary compensation for these tests. Assessments and the group fitness program will be conducted in at the Center for Health and Human Performance (directed by Co-Investigator [name]

[name]) at the Institute for Food, Nutrition, and Health on Rutgers Cook Campus in New Brunswick. This is a facility equipped with appropriate equipment and space for group exercise. The trainer will be a qualified professional trainer or member of the Center for Health and Human Performance with appropriate experience and expertise who will be closely supervised by [name] and the PI.

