TLC FIT (Technology-Enhanced Intervention): TLF FIT is composed of the group fitness program, use of an electronic accelerometer, private Facebook group and the mobile app. The group fitness program is manualized and will be led by a qualified trainer. The PI will teach the trainer the manualized program and treatment integrity will be evaluated during the program. The group program has four primary components: (1) cancer-specific and general educational modules, (2) physical exercise, (3) goal-setting and self-monitoring, and (4) social support. The original program consisted of eight weekly group sessions; however, participants expressed interest in adding exercise sessions, which would likely increase the impact on participants’ fitness. Therefore, the program is now 8 weekly group sessions lasting 90 minutes each plus 4 weeks of using the app without in-person groups. In-person sessions will consist of approximately 20 minutes of education regarding fitness and administrative tasks, 10 minutes of goal-setting/monitoring, and 60 minutes of instructor-led exercise and cool-down (~30 minutes of aerobic exercise and 30 minutes of muscle strengthening and balance exercises). Exercises are age-appropriate and the intensity of participation is individualized – that is, any exercise can be modified to be more or less strenuous for each participant based on participants’ ratings of perceived exertion as well as any physical limitations due to cancer treatment (such as hip problems). The trainer will have experience in assisting teens and young adults in modifying exercises to a level appropriate to their current fitness and physical abilities. Participants will wear a commercially available electronic accelerometer daily throughout the intervention to self-monitor progress. Data from the accelerometer will be electronically extracted into the app for easy monitoring and sharing of goals/progress. Social support for physical activity will be fostered through group interactions at each session and group messaging within the app and Facebook private groups. During the follow-up period, participants continue to use the app, set physical activity goals, and monitor progress. We will remotely download data regarding app use weekly throughout the intervention and follow-up.

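### TLC FIT is delivered in groups but the Aim 3 and Aim 4 ANCOVA has no term for delivery group, so its standard errors and p-values will be too small if outcomes correlate within groups

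*Combined protocol and SAP*

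**What the plan says.** Participants are randomised individually, stratified by cohort and age (section 9.3). Recruitment is in waves, and "each arm will have 5-10 patients at a time" (section 4.1). The programme is "8 weekly group sessions lasting 90 minutes each plus 4 weeks of using the app without in-person groups". Peer influence is an intended ingredient: "Social support for physical activity will be fostered through group interactions at each session and group messaging within the app", with private Facebook groups as well. Wait-list participants receive the programme only after the 6-month assessment (section 4.2), and Aims 3 and 4 are tested at 3 months (sections 9.1 and 9.4).

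For Aim 3, "outcome scores at the post assessment will be compared using ANCOVA, controlling for baseline scores". The next sentence reads "To account for enrollment in cohorts, cohort will be included as a covariate", and goes on to say that the term is removed if not significant. For Aim 4 the plan names only ANCOVA. Section 9.2 bases the sample size on individuals: "With a sample size of 40 per group and alpha set at .05", it claims "80% power to detect a medium effect size (Cohen's $d = .32$) for differences between groups in muscular strength scores using ANCOVA". Neither 9.2 nor 9.4 mentions a group random effect, a cluster-robust standard error, an ICC or a design effect.

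**The concern.** At Time 3 the design is partially nested. TLC FIT participants have trained together and supported one another; controls have not been grouped for treatment. ANCOVA treats all participants as independent given the covariates. If some groups do better than others for reasons their members share, that variation enters the mean of the intervention arm, and the residual error term does not reflect it in full.

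The cohort covariate looks like a safeguard but addresses something else. It removes a shift common to both arms of a wave. A delivery-group effect is present in one arm only, so it behaves as cohort-by-arm variation and goes into the treatment contrast whether or not cohort is in the model.

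Two things are at stake: the false-positive rate of the Aim 3 and Aim 4 tests, and the width of the interval around the effect size. The second matters because section 9.2 names effect-size estimation as a focus and section 10.5 says the data will inform the sample size of a future R01 application.

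**Working it through.** **Inputs from the documents.** 40 evaluable per arm and alpha .05 (section 9.2; two-sided is assumed, since sidedness is not stated); 5-10 patients per arm at a time (section 4.1). If each cohort has one delivery group, which is inferred and not stated, 40 evaluable patients form 40/10 = 4 to 40/5 = 8 groups.

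**Assumed.** The ICC at Time 3 among TLC FIT participants in the same group, given baseline; range 0 to .10.

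**The plan's own figure.** With 40 per arm and 77 df, d = .32 gives about 29% power, not 80%. The d detectable at 80% power is .634, which is Cohen's f = .634/2 = .317. The stated figure is therefore met if .32 is Cohen's f, or if the baseline correlation is about .86. That is a separate matter. Here it only fixes the starting point, d of about .63 in units of the adjusted residual SD.

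**Standard error.** With m per group, the design effect in the intervention arm is DE = 1 + (m - 1) x ICC; in the control arm it is 1. The ratio of true to reported standard error is sqrt[(DE + 1)/2], and the approximate two-sided type I error is 2 x [1 - Phi(1.96/ratio)].

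| Groups | ICC | DE | SE ratio | Type I error |
|---|---|---|---|---|
| 8 of 5 | .02 | 1.08 | 1.020 | .055 |
| 8 of 5 | .05 | 1.20 | 1.049 | .062 |
| 8 of 5 | .10 | 1.40 | 1.095 | .074 |
| 5 of 8 | .02 | 1.14 | 1.034 | .058 |
| 5 of 8 | .05 | 1.35 | 1.084 | .071 |
| 5 of 8 | .10 | 1.70 | 1.162 | .092 |
| 4 of 10 | .02 | 1.18 | 1.044 | .061 |
| 4 of 10 | .05 | 1.45 | 1.107 | .077 |
| 4 of 10 | .10 | 1.90 | 1.204 | .104 |

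**Simulation of the test as planned**, with cohort kept only if its F-test gives p < .05 (6,000 to 8,000 null trials per setting, no shared cohort effect):

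| Groups | ICC 0 | ICC .05 | ICC .10 |
|---|---|---|---|
| 8 of 5 | .054 | .066 | .075 |
| 5 of 8 | not run in this set | .074 | .091 |
| 4 of 10 | .053 | .077 | .105 |

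Always keeping cohort leaves these error rates almost unchanged: .064 and .077 at ICC .05, and .076 and .105 at ICC .10, for 8 groups of 5 and 4 groups of 10. Under the planned rule cohort survived in only about 7-14% of trials at ICC .05-.10. With a shared cohort effect of 5% of variance, the planned test gave .051-.052 at ICC 0, .058-.062 at ICC .02, .064-.076 at ICC .05 and .078-.107 at ICC .10 for the same two layouts.

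**Cost of a correct analysis.** With K groups, the approximate Satterthwaite df is (DE + 1)^2 / [DE^2/(K - 1) + 1/39]. The detectable d is the noncentrality that gives 80% power at that df, times sqrt[(DE + 1)/40].

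- 5 of 8, ICC .05: df = 2.35^2/(1.35^2/4 + 1/39) = 11.5; d = 3.07 x .242 = .74.
- 5 of 8, ICC .10: df = 2.70^2/(1.70^2/4 + 1/39) = 9.7; d = 3.12 x .260 = .81.
- 4 of 10, ICC .05: df = 2.45^2/(1.45^2/3 + 1/39) = 8.3; d = 3.19 x .248 = .79.
- 4 of 10, ICC .10: df = 2.90^2/(1.90^2/3 + 1/39) = 6.8; d = 3.28 x .269 = .88.
- True ICC 0: d = .67 (5 groups) or .69 (4 groups), from the lost df alone.

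**The case against.** A reader might infer that the standard errors and p-values are too small as a matter of fact. The documents do not support that. The harm needs a positive ICC at Time 3, and none is given. Several features could hold it down. Exercise intensity is individualised, the programme is manualised, and treatment integrity is checked. Section 4.1 describes one trainer role at one named facility; if the same person leads every wave, trainer effects do not differ between groups. The last 4 of the 12 weeks have no in-person sessions, so Time 3 falls about a month after the groups last met. The Aim 3 outcomes are objective, baseline-adjusted and measured by masked assessors. At ICC .01 the simulated type I error is only .056-.058. All of this stands, and it is why the point is conditional. It does not make the ICC zero, and a programme built on group support gives no reason to assume that it is.

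A reader might also take one delivery group per cohort, or recorded group identifiers, as stated. Neither is; only cohort is named, as a stratum.

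A shared cohort effect left out of the model pulls the other way: ANCOVA without cohort gave .047-.048 at ICC 0. That offset is partial and does not remove the inflation at ICC .05-.10.

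Finally, section 9.2 says the primary aim is feasibility, Aim 2 is descriptive, and no decision rule hangs on the Aim 3 p-value. This lowers the consequence. It does not affect the use of the effect estimate and its interval to plan the next trial.

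**Conclusion.** The point holds in conditional form. The structural gap is in the documents: treatment is grouped in one arm at the analysed time point, the planned model has no term for it, and the droppable cohort covariate cannot supply one. The size of the harm is not in the documents. With 4-8 groups, one per cohort, and 40 per arm, the type I error is nominal at ICC 0, about .055-.07 at ICC .02, .06-.08 at ICC .05 and .07-.11 at ICC .10. The upper ends belong to few, large groups. Prespecifying an allowance for delivery group is worthwhile and needs little work. It is not a reason to doubt the feasibility aim.

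**What to change.** In section 9.4:

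- Keep cohort in the Aim 3 and Aim 4 models regardless of significance. This follows the stratification; it does not by itself cure the clustering.
- For Aims 3 and 4, prespecify an analysis that allows for delivery group. One option is a partially nested mixed model with a random intercept for group in the TLC FIT arm only and small-sample df (Satterthwaite or Kenward-Roger). Another is a cohort-level comparison, which held its type I error at .047-.055 in simulation. Either can be primary, or a prespecified sensitivity analysis over a stated ICC range.
- State how many delivery groups each cohort has, and record group membership.
- Report the ICC with its interval, and say that 4-8 groups estimate it poorly. With 5 groups of 8 and a true ICC of .05, the ANOVA estimate is zero or negative in about 41% of trials, and a typical 95% interval runs from -.07 to .58.

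In section 9.2, give the detectable effect over the same ICC range.

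The work is plan wording and one model term. The real cost is wider intervals and fewer df. The detectable d at 80% power rises from about .63 to .74 (ICC .05) or .81 (ICC .10) with 5 groups of 8, and to .79 or .88 with 4 groups of 10. Even if the true ICC is 0, it rises to about .67-.69. That price is the argument for using the sensitivity-analysis route if the sponsor prefers to keep ANCOVA as primary.

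### Randomisation is stratified by cohort and age group, but the Aim 3 ANCOVA keeps cohort only if it is significant and never includes age group; the cost is modest and conservative.

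*Combined protocol and SAP*

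**What the plan says.** Two sections name the same stratification factors. Section 4.1 states: "Randomization will be stratified by cohort (since enrolled in waves) and age (13-17 vs. 18-25"; section 9.3 states: "Randomization will be stratified by cohort (due to recruitment in waves) and age (13-17 and 18-25".

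For the Aim 3 fitness outcomes, section 9.4 says that the groups' 3-month scores "will be compared using ANCOVA, controlling for baseline scores", and that "cohort will be included as a covariate and removed if not significant". It does not say what counts as not significant, or whether one decision covers all the fitness outcomes. Age group appears in no analysis model anywhere in the document.

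For Aim 4 (HRQOL and fatigue), the intervention group is to improve more "than the wait-list control group at the 3-month assessment using ANCOVA". No covariates are listed, and the cohort sentence is not repeated there.

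**The concern.** Stratified randomisation balances the arms on the strata. If a stratum also predicts outcome, that balance makes the treatment estimate more precise, but the analysis gets credit for it only if the stratum is in the model. Otherwise its variance stays in the residual and the standard error is overstated.

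Both factors could matter here. Exercise is delivered in small groups within cohorts. The background section links younger age to more physical activity. Section 5.2 uses different activity guidelines below and above 18 and says that those guidelines set the exercise prescription.

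The second issue is pre-specification. Feasibility is the primary aim, but sections 6 and 9.4 label the fitness measures primary outcomes, and section 10.5 says the data will feed a sample size estimate for a later application. A residual variance that depends on which covariates survived a test is a poor input to that calculation.

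**Working it through.** **1. The plan's own power figure.** Section 9.2 says: "With a sample size of 40 per group and alpha set at .05" there is "80% power to detect a medium effect size", given as d = .32. Two-sided, the noncentrality is .32 × √(40/2) = 1.431, and power is Φ(1.431 − 1.96) = 29.8% (29.3% by noncentral t). About 80% is recovered if .32 is read as Cohen's f (d = .64, power 80.7%), or if the baseline-outcome correlation is about .86 to .87 (79.1% and 81.8%); the plan states neither. That is a separate problem. The age calculation below takes a design with nominal 80% power, so noncentrality δ = 1.96 + 0.842 = 2.802.

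**2. Cohorts and degrees of freedom.** Section 4.1: "10-20 participants will be randomized within cohorts, and each arm will have 5-10 patients at a time". With 88 enrolled, 88/20 = 4.4 and 88/10 = 8.8, so about 5 to 9 cohorts, or 4 to 8 df. Age group adds 1, giving 5 to 9. With 80 analysed, baseline-only ANCOVA leaves 80 − 3 = 77 error df; the full model leaves 72 to 68.

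**3. Leaving out age group.** Let R² be the share of residual variance, after baseline, that age group explains. The documents give no value, so 0%, 5% and 10% are assumed. With k = 1/√(1 − R²), balanced strata and the normal approximation:

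- interval width relative to the adjusted model: k
- actual type I error without age: 2 × P(Z > 1.96k)
- actual power without age: Φ((δ − 1.96)k)
- power with age: Φ(δk − 1.96)

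| R² | k | Type I error without age | Power without age | Power with age | Power lost |
|---|---|---|---|---|---|
| 0% | 1.000 | .050 | 80.0% | 80.0% | 0 |
| 5% | 1.026 | .044 | 80.6% | 82.0% | 1.4 points |
| 10% | 1.054 | .039 | 81.2% | 84.0% | 2.7 points |

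**4. The cohort rule alone.** In simulation (5,000 trials per setting), a cohort effect worth 5% of residual variance was kept in 25% of trials with 5 cohorts and 21% with 8; at 10%, in 43% and 38%. So a modest real effect is usually dropped. The power cost is small: with 5 cohorts, always adjusting against pretesting gave 78.3% against 77.9%, and 79.6% against 79.3%.

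**5. Both features together.** A second simulation used 88 randomised within cohort-by-age strata and 10% lost. It assumed a baseline correlation of 0.6, an effect of 0.64 residual SD, 63% aged 18 or over, and p < .05 as significant. Each cell gives results for 5 / 9 cohorts.

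| Cohort share, age share | Type I error, plan's rule | Power, plan's rule | Power, both strata fixed |
|---|---|---|---|
| 0%, 0% | 4.9% / 5.0% | 77.6% / 79.6% | 77.2% / 77.5% |
| 5%, 5% | 4.7% / 4.5% | 82.7% / 81.7% | 83.8% / 82.8% |
| 10%, 10% | 4.5% / 3.8% | 84.1% / 82.9% | 87.6% / 86.0% |

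Type I error was 4.8-5.3% with both strata fixed. At an age share of 20% with cohort at 5%, an extreme assumption, the plan's rule had type I error of 3.0-3.2% and lost about 5 to 6 points.

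**6. Price of always adjusting.** Counting degrees of freedom only, with .32 read as f and N = 80, power is 80.7% with baseline alone and 80.6% with age and eight cohort terms added. The 0%, 0% row also reflects imbalance from small strata and dropout: the fixed model gives up 0.4 points with 5 cohorts and about 2 with 9. Each power figure has a simulation standard error of about √(.78 × .22/2,500) = 0.8 points.

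**The case against.** The strongest reply is that little is at risk. Stratification balances cohort across the arms, so keeping or dropping it barely moves the estimate, and the rule tests cohort rather than treatment. Baseline score already absorbs much of the difference between a 13-year-old and a 25-year-old; only age variance beyond baseline counts, and it could be near zero. The background links age to physical activity, not to change in strength or estimated VO2max. Section 9.2 also says feasibility is the primary aim, and slightly wide intervals are unlikely to change a pilot's conclusions. All of this stands, and it is why the range starts at 0% and the point is graded low.

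The mismatch with the design remains, as does a data-dependent choice with no threshold.

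A reader might infer more than the documents support:

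- *The cohort test is run outcome by outcome, giving each outcome its own model.* Section 9.4 does not say whether it is run once or several times.
- *The rule also governs HRQOL and fatigue.* It is written only under Aim 3. The gap in Aim 4 is that covariates are not stated.
- *The primary model is open until the data are seen.* Baseline is fixed and only cohort is in play, so there are two candidate models.

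**Conclusion.** The point holds as a mismatch between design and analysis, plus an incompletely specified covariate rule. Its severity is minor to moderate.

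It would be wrong to read this as biased estimates or excess false positives: every scenario examined put type I error under the plan's rule at or below about 5%. It would also be wrong to set 80% power against 82-84% and call the difference the loss. Under stratified randomisation the test without age already has 80.6-81.2%, so the loss is about 1 to 3 points at an age share of 5-10%, and none at 0%.

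The textual finding is certain. The size rests on assumed variance shares and on a nominal 80% power that the printed d = .32 does not deliver.

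**What to change.** Replace the cohort sentence in section 9.4 with: *The ANCOVA for every Aim 3 and Aim 4 outcome will include baseline score, cohort and age stratum (13-17 vs 18-25); cohort and age stratum are randomisation factors and will be retained regardless of statistical significance.*

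This costs one sentence and 5-9 of the 77 error degrees of freedom, with no change to sample size, randomisation or conduct. If the strata prove uninformative, the price is somewhere between nothing and about 2 points of power, highest with many small cohorts. If many small cohorts are expected, cohort could be pre-specified as a random effect instead. Either choice should be fixed before outcome data are examined.
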